2.5.2 Statistical hypothesis, model, and method of analysis

No inferential statistical methods are planned. Descriptive statistics will be used to summarize data.

Retreatment efficacy of ligelizumab 120 mg q4w or 72 mg q4w in achieving well-controlled CSU at Week 12 in the first half of the treatment period will be evaluated in subjects transitioning from the core studies. The primary analysis will be performed for subjects receiving the same dose of ligelizumab they received in the core studies, i.e. 72 mg or 120 mg for one year.

For subjects rolling over from study CQGE031C2302 and CQGE031C2303 (i.e. two core studies) and treated with same ligelizumab dose regimen, summary statistics for the proportion of subjects achieving $UAS7 \leq 6$ response will be provided by treatment group in core studies, and by visit starting from Visit 201 up to Visit 204 (i.e. Week 12 of the first half of the treatment period). The corresponding 95% confidence interval for response rate also will be derived based on the score method including continuity correction (Newcombe, 1998).

For the subgroup of subjects who achieved $UAS7 \leq 6$ at Week 12 in the core studies, and who received either 72 mg or 120 mg ligelizumab, the proportion of subjects with the response of $UAS7 \leq 6$ at Week 12 of the first half of the treatment period in this extension study will be provided together with a 95% confidence interval.

Subjects rolling over from study CQGE031C2302 and CQGE031C2303, who received different treatment or different ligelizumab dose regimen, will not be included in the primary analysis for re-treatment efficacy.

Subjects rolling over from study CQGE031C1301, who received ligelizumab 120 mg, will not be included in this primary analysis.

Subjects rolling over from the adolescent PK/PD study CQGE031C2202 will also not be included in this primary analysis, as they received treatment doses of ligelizumab of 24 mg or 120 mg for different treatment times.

2.5.3 Handling of missing values/censoring/discontinuations

The UAS7 score is derived from the sum of the HSS7 score and the ISS7 score, as noted above. The HSS7 and ISS7 score will be derived by adding up the daily HSS and ISS scores of the 7 days preceding the visit, respectively. The daily score (HSS and ISS) will be calculated by averaging the morning and evening HSS and ISS score, respectively. If one of the morning or evening scores is missing, the non-missing score for that day (morning or evening) will then be used as the daily score.

A minimum of 4 out of 7 daily scores are needed to reliably calculate a weekly HSS7, ISS7 or UAS7 score. For each weekly score from UPDD (i.e. HSS7, ISS7 and UAS7 score), if one or more of the daily scores are missing, the following principles will be applied to handle the missing data:

- If a subject has at least 4 “non-missing” daily scores within the 7 days prior to the study visit, the weekly score will be calculated as the sum of the available eDiary scores of that week, divided by the number of non-missing days, multiplied by 7.
- If there are less than 4 “non-missing” daily scores within the prior 7 days, then the weekly score will be considered as missing for that week.

Subjects who discontinue from study treatment early will be encouraged to stay in the study following the procedures described in the study protocol Section 9.1.1. These are considered as retrieved dropout (RDO) subjects.

The primary analysis will account for different post-dosing events for missing data handling as follows:

- Discontinuation of initially assigned study treatment prior to Week 12 (Visit 204) due to AEs or lack of efficacy or any other reasons, except for the reason of study early termination: Retrieved dropout (RDO) data collected after study treatment discontinuation will be used for analysis. If no RDO data was collected after study treatment permanent discontinuation, non-responder imputation will be applied for missing data imputation.
- Discontinuation of initially assigned study treatment prior to Week 12 (Visit 204) due to study early termination: the efficacy data collected after the discontinued treatment will be censored. The missing data caused by this intercurrent event occurrence will be imputed based on the treatment arm (ligelizumab 72 mg or 120 mg q4w) data under the missing at random (MAR) assumption using multiple imputation separately.
- Use of protocol allowed rescue medication prior to Week 12 of the first half of the treatment period (V204): Efficacy data collected during intake of rescue medication will not be excluded from the analysis. H1-AH is being used as rescue medication in addition to background medication. Considering that, the patient population are refractory to H1-

AHs and that ligelizumab efficacy is being evaluated on top of H1-AH therapy, all data collected will be used for analysis.

For missing or censored UAS7/HSS7/ISS7 scores due to all other reasons, non-responder imputation will be applied for missing data imputation.

Multiple imputation (MI)

Multiple imputation is a simulation based approach where missing values are replaced by multiple Bayesian draws from the conditional distribution of missing data given the observed data and covariates, creating multiple completed data sets. These completed data sets can then be analyzed using standard methods. Rubin (1987) presented rules how to combine the multiple sets of estimates to produce overall estimates and confidence intervals that adequately incorporate missing data uncertainty. The multiple imputation analysis will be imputed based on the individual treatment arm information.

Missing values for the “change from baseline UAS7 score” will be imputed separately for each treatment group including region, CU index and baseline UAS7 score in the model.

Specifically, the missing data will be imputed following the steps below:

1. Impute the following missing data which will be used for primary analysis following the MAR assumption.
 - The intermittent missing data;
 - Missing data with intercurrent events handled through hypothetical strategy.

The missing data not fit in to the categories above will not be imputed in this step.

The imputed results will be transferred back for the imputed values on the primary endpoint “proportion of $UAS7 \leq 6$ at week 12.”

2. Impute the rest missing data of the primary efficacy endpoint with non-responder imputation.

Duplicate data handling of questionnaires

For HSS7, ISS7, the daily score is derived from the average of morning and evening scores. All other questionnaires are completed either daily or at visits. If any of those questionnaires are completed more than once per day or visit (depending on the questionnaire schedule), then the worst outcome (i.e. the highest score) of the duplicate observations will be used in the analysis.

2.6 Analysis of the key secondary objective

For retreatment efficacy evaluation (based on subjects who roll-over from C2302/C2303 and in the retreatment subpopulation):

- To describe the efficacy of ligelizumab 72 mg or 120 mg q4w in achieving complete control of chronic spontaneous urticaria (CSU) at Week 12 when used as retreatment
- To describe the efficacy of ligelizumab with respect to a reduction from extension study baseline in the UAS7 and its components (weekly itch severity score (ISS7) and weekly hives severity score (HSS7) at Week 12

- To describe the efficacy of ligelizumab in achieving an angioedema-free period at Week 12
- To describe the efficacy of ligelizumab in achieving Dermatology Life Quality Index (DLQI) = 0-1 at Week 12 when used as re-treatment

For self-administration efficacy evaluation (based on subjects who roll-over from all preceding studies and in the self-administration subpopulation):

- To describe the efficacy of ligelizumab in the treatment of CSU, 12 weeks after starting out-of-clinic self-administration

2.6.1 Key secondary endpoints

For all secondary efficacy analyses, the FAS (or subpopulations within FAS) will be used. All listings and tables will be presented by treatment group unless stated otherwise. All data will be included in the analysis regardless of rescue medication use.

All secondary analyses to be performed in this study are described and summarized in

Table 2-9.

Table 2-9 Overview of analyses on secondary efficacy endpoints

Analysis Population and Analysis Period/time point	Endpoints and Analysis
Objective: to assess the retreatment efficacy of ligelizumab	

population: Ligelizumab retreatment subpopulation
 
period/time point: TRT1A/Visit204 (Week 12)
	
 • The proportion of subjects with completely controlled urticaria (UAS7 = 0) at Week 12 • Absolute change from extension study baseline in the UAS7 and its components (ISS7 and HSS7) at Week 12 • Cumulative number of weeks that subjects achieve weekly angioedema activity score (AAS7) = 0 between extension study baseline and Week 12 • Percentage of subjects achieving DLQI = 0-1 at Week 12
Objective: to assess the self-administration efficacy	

Population: self-administer subpopulation, who have at least one self-administration in TRT1B
 
Period/time point: 12 weeks after starting outside-clinic self-administration in TRT1B
	
 • The proportion of subjects with well-controlled disease (UAS7 ≤ 6), 12 weeks after starting self-administration

- Percentage of subjects achieving UAS7 = 0 (complete control of urticaria) at week 12 after retreatment of ligelizumab for subjects receiving the same dose regimen as in the core studies.

The proportion of subjects with UAS7 = 0 at Week 12 will be summarized in a descriptive manner, it will be provided together with 95% Clopper-Pearson exact confidence interval.

Similar missing data imputation rules as the primary endpoint analysis will be applied in this secondary efficacy endpoint analysis. The missing data imputation will be based on the proportion of subject with UAS7 = 0 at week 12.

- Absolute change from extension study baseline in UAS7 at Week 12 after retreatment of ligelizumab for subjects receiving the same dose regimen as in the core studies.

The absolute change from extension study baseline in UAS7 score at Week 12 will be summarized descriptively, it will be provided together with 95% confidence interval. The change from extension study in UAS7 components (ISS7 and HSS7) will also be provided in descriptive manner at Week 12.

Similar missing data imputation rules as the primary endpoint analysis based on change from baseline in UAS7 score at week 12 will be used for this secondary endpoint analyses. The imputations for ISS7 and HSS7 will follow the same missing data imputation rules.

- Percentage of subjects achieving DLQI = 0-1 (no impact on subjects QoL) at Week 12 after retreatment of ligelizumab for subjects receiving the same dose regimen as in the core studies.

An overall score will be calculated according to the scoring manual. The proportion of subjects with overall DLQI scores ≤ 1 at Week 12 will be summarized in a descriptive manner, it will be provided together with a 95% Clopper-Pearson exact confidence interval. Similar missing data imputation rules as the primary endpoint analysis will be applied in this secondary efficacy endpoint analysis. The missing data imputation will be based on the proportion of subject with UAS7 = 0 at week 12.

- Cumulative number of weeks that subjects achieve AAS7 = 0 between extension study baseline and Week 12

The cumulative number of weeks achieving AAS7 = 0 response between baseline and Week 12 will be derived based on the AAS eDiary. A weekly AAS7 score will be derived by adding up the daily scores of the 7 days preceding the visit, and ranges from 0 to 105. For a weekly AAS7 score, if one or more of the daily scores are missing, the same principles as handling the weekly score from UPDD will be applied to handle the missing data. If the AAS7 score is missing, similar missing imputation rules as the primary analysis will be applied on AAS7 = 0 proportion over the first 12 weeks. The imputed AAS7 = 0 will be used for the cumulative number of weeks that subjects achieve AAS7 = 0 response calculation. The cumulative frequency plot will be provided together with the summary statistics.

- Percentage of subjects achieving UAS7 ≤ 6 (well-controlled urticaria) at 12 weeks after starting self-administration in the first half of the treatment period.

The proportion of subjects with UAS7 ≤ 6 , 12 weeks after starting self-administration will be summarized in a descriptive manner, and it will be provided together with 95% Clopper-Pearson exact confidence interval. Missing data will be considered as non-responder in the analysis.

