2.6.3 Handling of missing values/censoring/discontinuations

Missing data handling for HSS7, ISS7, and UAS7 score

Refer to Section 2.5.3.

Missing data handling for AAS7 score

The weekly score AAS7 will be derived by adding up the daily scores of the 7 days preceding the visit. The weekly score will then range from 0 to 105.

For each weekly score from AAS, if one or more of the daily scores are missing, then the following principles will be applied to handle the missing data:

- If a patient has at least 4 non-missing daily scores within the 7 days prior to the study visit, then the weekly score will be calculated as the sum of the available eDiary scores of that week, divided by the number of non-missing days multiplied by 7.
- If there are less than 4 non-missing daily scores within the prior 7 days, then the weekly score will be missing for that week.

Missing data handling for DLQI score

There was a very high success rate of accurate completion of the DLQI. However, if responses were incomplete, the following rules were applied:

1. If one question was left unanswered, then the missing value was imputed to a 0 score and the overall DLQI/CDLQI score was summed up in the usual way out of 30.
2. If two or more questions were left unanswered, then the questionnaire was not scored (left to missing).
3. If question no. 7 was answered 'yes', then it was scored to a value of '3'. If question no. 7 was answered 'not relevant' then the score was 0. If question was answered 'no' (not being preventing to work or study) but the skin was a problem for working or studying, then the scores per possible response were either 'a lot' (2) or 'a little' (1) or not at all (0).

Missing data imputation for UAS7=0, UAS7≤ 6, DLQI=0-1, and AAS7=0 response

In analyses of above mentioned secondary efficacy endpoints, missing values with respect to response variables based on UAS7 score, DLQI/CDLQI score will be imputed as described in Section 2.6.1.

Multiple imputation methods refer to Section 2.5.3.

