5.5.2.2 Secondary analysis for binary endpoints

For binary endpoints of UAS7=0/DLQI 0-1 at Week 12, the secondary analysis will be performed based on the data after the missing data imputation for the intercurrent events has been performed.

The SAS procedure `proc mi` will be used for multiple imputation with the following sample code:

```
proc mi data=... out=... nimpute=... seed=123;  
by group;cuin  
class ige cuind group week12;  
fcs logistic (week12 = ige cuind group baseline / details);  
var ige cuind group baseline week12;  
run;  
where group = treatment group  
    ige = baseline IgE
```

cuind = baseline CU index
baseline = baseline UAS7 score
week12 = binary response of UAS7=0/DLQI 0-1 at Week 12 in TRT1.

If the imputation model does not converge, remove the covariates as needed until it converges.

The SAS procedure `proc freq`, and `proc mianalyze` will be used for the analysis. Sample code refer to Section 5.5.1. Wilson score method is not necessary for 95% confidence limits calculation in secondary analysis. Other methods could be performed as needed.

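### SAP 2.6.1 and 5.5.2.2 give incompatible intervals for the multiply imputed UAS7 = 0 and DLQI 0-1 endpoints, and the one named in 2.6.1 has no between-imputation term

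*SAP*

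**What the plan says.** SAP 2.6.1 names the interval for two binary Week 12 endpoints. For UAS7 = 0, "it will be provided together with 95% Clopper-Pearson exact confidence interval". For DLQI 0-1, "it will be provided together with a 95% Clopper-Pearson exact confidence interval". Each paragraph then adds: "Similar missing data imputation rules as the primary endpoint analysis will be applied in this secondary efficacy endpoint analysis".

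Those rules are in SAP 2.5.3. Step 1 multiply imputes, under missing at random, intermittent gaps and "Missing data with intercurrent events handled through hypothetical strategy", meaning stops before Week 12 caused by the early termination of the study. The remaining missing values are set to non-response. The section says Rubin's rules give "overall estimates and confidence intervals that adequately incorporate missing data uncertainty". For the secondary endpoints, SAP 2.6.3 sends the reader back: "Multiple imputation methods refer to Section 2.5.3".

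SAP 5.5.2.2 covers the same two endpoints: "For binary endpoints of UAS7=0/DLQI 0-1 at Week 12, the secondary analysis will be performed based on the data after the missing data imputation". It uses proc mi, then proc freq and proc mianalyze as in 5.5.1. On the interval it says: "Wilson score method is not necessary for 95% confidence limits calculation in secondary analysis. Other methods could be performed as needed". It does not mention Clopper-Pearson.

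Only the primary endpoint has a written imputation-adjusted interval, the Wilson formula in 5.5.1. The self-administration endpoint in 2.6.1 also gets Clopper-Pearson, but there all missing data count as non-response. SAP 2.14.4 and Table 2-16 keep UAS7 = 0 and DLQI 0-1 in the final analysis.

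**The concern.** A Clopper-Pearson interval is built from one responder count out of n, all treated as observed. It has no term for the spread between imputed data sets. Section 2.6.1 does not say how the interval is formed over m completed data sets, so a programmer following it would use either one data set or the averaged count. Both treat imputed responses as real ones. A programmer following 5.5.2.2 would report a pooled interval and not meet 2.6.1.

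Protocol 12.5.1 treats missing UAS7 = 0 and DLQI data as non-response, and an exact binomial interval is coherent under that rule. The SAP change log records that multiple imputation was added to some secondary endpoints in Amendment 2. My inference is that the interval wording was not brought into line.

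At stake is the precision reported for two secondary endpoints. No test is planned, so the interval is the stated measure of uncertainty.

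**Working it through.** **1. The plan's own interval figures.** The documents give no interval for UAS7 = 0 or DLQI 0-1. The nearest is SAP Table 3-1 (UAS7 ≤ 6, 55% response, 10% dropout). With n = 0.9N and p ± 1.96√(p(1−p)/n):
- N = 250: 124/225 gives 48.6%-61.6%
- N = 450: 223/405 gives 50.2%-59.9%
- N = 600: 297/540 gives 50.8%-59.2%

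All six limits match. The table is used here only to set a realistic n.

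**2. Inputs.** n = 225 is the first row of Table 3-1 after dropout. The rate p = 44% is the UAS7 = 0 proportion after the third 72 mg dose in the Phase IIb study (Protocol 4.1.1). A rate of 30% was also run, close to the 29.8% after the first dose. The imputed fraction f is not in the documents, so 0% to 40% is assumed.

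**3. Closed form.** Let r = (1 + 1/m)B/U, with B the between-imputation and U the within-imputation variance. Without strong covariates r ≈ f/(1−f), so 1 + r = 1/(1−f) and the effective sample size is n/(1 + r) = n(1−f). Clopper-Pearson on the completed data ignores this and stays at 37.4%-50.8%, width 13.34 points, for every f.

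| f | n(1−f) | Width with imputation variance (points) | Shortfall of 13.34 |
|---|---|---|---|
| 2% | 220.5 | 13.48 | 1% |
| 5% | 213.8 | 13.70 | 3% |
| 10% | 202.5 | 14.08 | 5% |
| 20% | 180.0 | 14.95 | 11% |
| 30% | 157.5 | 16.01 | 17% |
| 40% | 135.0 | 17.32 | 23% |

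**4. Coverage by simulation.** Values missing at random within arm, m = 50, p = 30% and 44%. The averaged-count column uses n = 150 and 300 (10,000 to 20,000 replicates). The single-data-set column uses n = 225 and 450 (4,000 replicates).

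| f | Clopper-Pearson, averaged count | Clopper-Pearson, one completed data set |
|---|---|---|
| 2% | 95.2-95.7% (2% and 5% together) | 95.0-96.3% |
| 5% | as above | 94.2-95.6% |
| 10% | 94.1-94.9% | 92.8-94.3% |
| 20% | 92.5-93.2% | 90.0-90.8% |
| 30% | 90.6-91.3% | 85.5-87.8% |
| 40% | 87.9-88.7% | 79.9-82.9% |

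The Rubin-pooled interval covers 93.5-95.3% throughout at n = 225 and 450. A pooled Wilson interval without continuity correction covers 94.7-95.3% at n = 150 and 300.

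**5. Can the primary endpoint's formula be borrowed?** Not as printed in SAP 5.5.1. It sets t at the 95% quantile, which makes a 90% two-sided interval. It also puts the upper-limit continuity term (estimate + 1/(2n)) into both limits. Take n = 150, estimate 0.44, f = 30%, so r = 0.3/0.7 = 0.4286:
- As printed, t ≈ 1.645 and t²(1 + r)/n = 0.0258. Centre = (0.88 + 0.0067 + 0.0258)/(2 × 1.0258) = 0.4448. Half-width = √(0.19781 − 0.19161) = 0.0787. Width = 0.157.
- With t ≈ 1.96 and no continuity term, t²(1 + r)/n = 0.0366 and the width is about 0.187.
- With t ≈ 1.96 and a separate continuity term for each limit, the limits are 0.346 and 0.539, width 0.193.

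Clopper-Pearson in the same setting has width 0.163. The printed formula is therefore narrower than the interval it would replace, and its simulated coverage is 89.5-90.4% at every f tested. The properly continuity-corrected version covers about 96%.

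**The case against.** The strongest reply is that the SAP does plan pooling. Section 2.5.3 describes Rubin's rules, 2.6.3 refers to them for the secondary endpoints, and 5.5.2.2 names proc mianalyze for exactly these two. On that route the imputation variance is carried. This stands. A reader might infer that the reported intervals will certainly be too narrow, but the documents support that only if 2.6.1 is followed on completed data. The contradiction between the sections remains either way.

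Second, the imputed share may be small. Multiple imputation covers only early-termination stops before Week 12 and intermittent gaps. At about 5% or less, Clopper-Pearson's built-in conservatism offsets the missing variance. This also stands, and nothing in the documents shows the share reaching 20%.

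Third, a reader might infer that Clopper-Pearson cannot be computed after imputation because it needs an integer count. That is too strong: its beta-quantile form accepts non-integer counts, and an effective-sample-size version exists, as used in the closed form above. The SAP describes neither.

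Fourth, SAP 2.6.2 plans no inference on these endpoints, so leaving the method open cannot change a test result. It still leaves the reported interval undefined.

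**Conclusion.** The point holds as an inconsistency with a conditional statistical cost. SAP 2.6.1 and 5.5.2.2 cannot both be followed for UAS7 = 0 and DLQI 0-1, whatever share is imputed. If 2.6.1 is followed on completed data, the loss of coverage is negligible up to about 5% imputed and at most about 1 point at 10% on the averaged count. It is about 2 to 3 points at 20%, 4 at 30% and 7 at 40%, and larger if a single completed data set is used.

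These sizes assume data missing at random within arm, weak covariates, and true rates of 30% to 44%. The imputed share is an assumed range. Only the descriptive error bars are affected; no hypothesis test or decision rule depends on them. The self-administration endpoint is not affected, because non-responder imputation creates no between-imputation variance.

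**What to change.** - In SAP 2.6.1 and 5.5.2.2, name the same Rubin-pooled two-sided 95% interval for UAS7 = 0 and DLQI 0-1. One choice is the imputation-adjusted Wilson interval with t at the 97.5% quantile and, if continuity-corrected, a separate continuity term for each limit. Do not carry over the 5.5.1 formula as printed.
- Delete the sentence in 5.5.2.2 that allows other methods as needed.
- Keep Clopper-Pearson only for the self-administration endpoint.
- Report the number of values multiply imputed per arm beside each interval, so that the reader can judge how much the imputation matters.

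The cost is SAP wording and a small programming change. No new data are needed. The downside is slightly wider intervals: at n = 225, 44% response and 20% imputed, mean width rises from 13.3 points to 14.5 (Rubin) or 14.8 (pooled Wilson with continuity correction).

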5.5 Statistical models and SAS sample code

5.5.1 Primary analysis

The primary analysis will be performed based on the data after the missing data imputation for the intercurrent events has been performed.

Step 1:

The SAS procedure `proc mi` will be used for multiple imputation for change from baseline in UAS7 score with the following sample code:

```
proc mi data=... out=... nimpute=... seed=123;  
by group;  
class ige cuind group;  
fcs reg(/details);  
var ige cuind group baseline wk12cfb;  
run;
```

where `group` = treatment group
`ige` = baseline IgE
`cuind` = baseline CU index
`baseline` = baseline UAS7 score
`wk12cfb` = change from baseline UAS7 score at Week 12 in TRT1.

If the imputation model does not converge, remove the covariates as needed until it converges.

The following SAS sample code will be used to transfer the continuous variable change from baseline in UAS7 score to a binary response of $UAS7 \leq 6$, and conduct non-responder imputation for subjects who discontinued due to study early termination:

```
data ...;  
set ...;  
resp = (baseline + wk12cfb) <= 6;  
if flag = 0 then resp = 0;  
run;
```

where `resp` = binary response of $UAS7 \leq 6$
`baseline` = baseline UAS7 score
`wk12cfb` = change from baseline UAS7 score at Week 12 in TRT1
`flag` = flag of missingness
(1 = missing due to study early termination, 0 = missing not due to study early termination, . = data is observed).

Note that the order of multiple imputation and non-responder imputation could be reversed as needed.

Step 2:

The SAS procedure `proc freq` will be performed to calculate the primary endpoint (binary response of $UAS7 \leq 6$ at Week 12) for each imputed dataset with the following sample code:

```
proc freq data = ...;  
by _imputation_group;  
tables resp /nopercnt nocol norow nocum binomial(level = "1" cl =  
wilson(correct));  
output out = sumstat binomial;  
run;
```

where `_imputation_` = the index for imputation times

group = treatment group

resp = binary response of UAS7≤6

sumstat is the dataset which includes the response rate estimate and the standard error in each group

Here “cl = wilson(correct)” is used to calculate the 95% confidence intervals by Wilson score method with continuity correction.

Step 3:

Rubin’s Rule:

Rubin’s Rule will be applied to combine the multiple sets of estimates to produce the overall estimates, standard error, confidence interval and p-values.

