5.5.2 Key secondary analysis

5.5.2.1 Secondary analysis for continuous endpoints

For continuous endpoints of change from extension study baseline in UAS7/HSS7/ISS7 score at Week 12, the secondary analysis will be performed based on the data after the missing data imputation for the intercurrent events have been performed.

The SAS procedure `proc mi` will be used for multiple imputation. Sample code refer to Section 5.5.1.

The SAS procedure `proc means` will be used to calculate the group means for each imputed dataset with the following sample code:

```
proc means data = ...;  
by _imputation_ group notsorted;  
var wk12cfb;  
Output out = sumstat mean = meancfb std = stdcfb;  
run;  
where _imputation_ = the index for imputation times  
    group = treatment group  
    wk12cfb = change from baseline UAS7/HSS7/ISS7 score at Week 12 in TRT1  
    sumstat is the dataset which includes the mean estimate (meancfb) and the standard error (stdcfb) in each group.
```

The SAS procedure `proc mianalyze` will be used to combine the parameter estimates across imputed datasets with the following sample code:

```
ods output ParameterEstimates = pe_comb;  
proc mianalyze data = sumstat;  
by group;  
ModelEffects meancfb;  
stderr stdcfb;  
run;
```

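### Non-responder imputation has no defined value for change in UAS7, ISS7 and HSS7, so subjects who stop early without retrieved data do not lower the reported mean reduction

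*SAP*

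**What the plan says.** SAP 2.6.1 sets the rule for absolute change in UAS7 by reference: "Similar missing data imputation rules as the primary endpoint analysis based on change from baseline in UAS7 score at week 12 will be used". It adds: "The imputations for ISS7 and HSS7 will follow the same missing data imputation rules".

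The primary rules it points to are in SAP 2.5.3:

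- **Discontinuation for adverse events, lack of efficacy or any other reason except study termination.** "Retrieved dropout (RDO) data collected after study treatment discontinuation will be used for analysis". Failing that: "If no RDO data was collected after study treatment permanent discontinuation, non-responder imputation will be applied for missing data imputation".
- **Discontinuation because the study was terminated.** "The missing data caused by this intercurrent event occurrence will be imputed based on the treatment arm", under MAR by multiple imputation.
- **Scores missing for all other reasons.** Non-responder imputation, named for UAS7, HSS7 and ISS7 scores.

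The multiple-imputation part of 2.5.3 then has two steps. Step 1 imputes intermittent gaps and hypothetical-strategy data under MAR, and excludes everything else. Step 2 reads: "Impute the rest missing data of the primary efficacy endpoint with non-responder imputation".

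In the sample code, SAP 5.5.1 runs `proc mi` on `wk12cfb`, derives the binary `resp`, and overrides it with "if flag = 0 then resp = 0". For the continuous endpoints, SAP 5.5.2.1 says the same procedure "will be used for multiple imputation. Sample code refer to Section 5.5.1". It then goes to `proc means` and `proc mianalyze`.

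No other section fills the gap. The imputation paragraph of SAP 2.6.3 covers response variables only, SAP 2.14.8 refers back to 2.5.3 and 2.6.3, and Protocol 12.5.1 gives no imputation rule for this endpoint.

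**The concern.** Non-responder imputation assigns a category. It works for UAS7 ≤ 6, but a change score needs a number and the SAP gives none. The analyst would have to choose one with data in hand, and the two sources of guidance, text and code, point in different directions.

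The subjects concerned are those most likely to have done badly. The primary estimand (SAP 2.5.1.1) confines the hypothetical strategy to study termination and treats other discontinuations under treatment policy. Giving those other subjects a same-arm MAR value extends the hypothetical approach to them without saying so. Leaving them out has much the same effect on the mean.

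The same subject could then be a failure in the UAS7 ≤ 6 table and, in the change table, either carry a treated-arm change score or be absent. The study has no placebo or active comparator (Protocol 4.3 and 6.1.1), so the within-arm mean is the whole result for this endpoint.

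**Working it through.** **Step 1. Trace one subject.** Take a subject who stops before Week 12 for lack of efficacy and has no retrieved data.

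| Source | UAS7 ≤ 6 (primary) | Change in UAS7 |
|---|---|---|
| SAP 2.5.3 text | Outside step 1; non-responder in step 2 | Outside step 1; step 2 covers only the primary endpoint, so the score stays missing and leaves the mean |
| SAP 5.5.1 and 5.5.2.1 code | MAR draw, then `resp` set to 0 because `flag` = 0 | MAR draw kept; the override acts on `resp`, not on `wk12cfb` |

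The `proc mi` call has no condition on the reason for missingness, so the code imputes every missing `wk12cfb`. Neither column-three route registers the failure.

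**Step 2. Inputs for size.**

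- The plan states no mean, SD or expected value for change in UAS7, so there is no figure of its own to reproduce for this endpoint.
- Drop-out by Week 12 is 10% (Protocol Table 12-1, SAP Table 3-1). As a check on how that 10% is used, the table's intervals were recomputed after removing it: 124/225, 223/405 and 297/540 give Wald 95% intervals of 48.6–61.6%, 50.2–59.9% and 50.8–59.2%. All three match, so 10% is total drop-out.
- Mean change in subjects with data, *m*: assumed -15 to -25 points.
- Share affected (non-termination stop, no retrieved data), *d*: unknown; at most 10% on the planning figure. A value of 2% is shown as a low case.

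**Step 3. Formula.** With affected subjects omitted, the mean is *m*. With zero change for them, it is (1 − *d*) × *m*. The gap is *d* × |*m*|.

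| *d* | \|*m*\| = 15 | \|*m*\| = 20 | \|*m*\| = 25 |
|---|---|---|---|
| 2% | 0.3 | 0.4 | 0.5 |
| 10% | 1.5 | 2.0 | 2.5 |

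If affected subjects in truth kept half the improvement, the gap would halve: 0.10 × 15/2 = 0.75 to 0.10 × 25/2 = 1.25 at 10%.

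**Step 4. Do the two readings differ?** The `proc mi` step was simulated within one arm: 250 subjects, assumed mean change -20 in subjects with data, drop-outs with true mean change zero, no retrieved data, and baseline UAS7, CU index and IgE in the model. At 10% drop-out the mean was -19.97 by the code, -19.98 with drop-outs left missing, and -17.96 with zero change. At 5% it was -20.02, -20.02 and -19.03. Text and code give nearly the same point estimate, and both differ from zero change by about *d* × 20.

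**The case against.** The strongest objections are these.

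- **The plan does not say that these subjects are imputed as average completers.** A reader might infer it from the code. The documents do not support it as a flat statement. The code is labelled as sample code, step 1 of 2.5.3 excludes these subjects from MAR imputation, and the draws are conditional on baseline covariates in a model that includes retrieved drop-outs with Week 12 data. This stands. The rule is undefined, with text and code implying different things.
- **Zero change is an assumption, not the truth.** Exclusion criterion 24 (Protocol 5.2) puts five half-lives at about 4 months, so someone who stopped after one or two doses may still be exposed at Week 12. This stands. The figures are a gap between two assumptions, not a proven bias. Subjects who stop for adverse events need not have responded poorly.
- **Few subjects may be affected.** Retrieved scores are used first, Protocol 9.1.1 asks sites to keep subjects in visits to Week 12, and termination-related stops properly receive MAR imputation. This stands, and it makes 10% an upper bound.
- **A 15% drop-out might be thought to apply.** That figure is the planning assumption for the prior-responder subgroup (Protocol 12.8.1, SAP 3.1). Change from baseline is planned in the full analysis set and the retreatment subpopulation (SAP Tables 2-9 and 2-16), so it is not used here.
- **The endpoint is secondary and descriptive.** SAP 2.6.2 plans no inference, and the primary result is untouched. This limits the consequence to a reported mean and its interval.

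None of this supplies the missing value or reconciles the code with the text.

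**Conclusion.** The point holds in this form: the continuous endpoints inherit a non-responder rule with no value on their scale, and both available readings let unretrieved, non-termination discontinuations pass without lowering the mean reduction. The direction is likely to favour the drug, because stops for lack of efficacy are among those affected.

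Against zero change, the gap is at most 1.5 to 2.5 UAS7 points if the whole 10% planned drop-out were affected, and 0.3 to 0.5 points at 2%. Both ranges rest on an assumed mean change of -15 to -25, no retrieved data in the affected share, and full return to baseline. The gap falls in proportion as any of these weakens.

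This is more than missing detail, because following the plan as written gives results at odds with its own handling of intercurrent events. It does not affect the primary analysis or any hypothesis test.

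**What to change.** In SAP 2.6.1 and 5.5.2.1, for change in UAS7, ISS7 and HSS7:

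1. Use retrieved data wherever they exist, as now.
2. Restrict MAR multiple imputation to the step 1 categories of 2.5.3: study termination and intermittent missing data.
3. For discontinuation for any other reason without retrieved data, impute return to baseline. This can be zero change, or a draw centred on the subject's baseline, which keeps imputation uncertainty that a fixed zero removes. Zero change agrees with the primary table for any baseline UAS7 above 6, which the entry threshold of 16 (Protocol 5.1) leads one to expect.
4. Drive this from a separate indicator for such discontinuations, applied before `proc means`. Do not reuse `flag` = 0. SAP 5.5.1 defines it as all missingness not due to termination, so it would also set zero change for on-treatment subjects with too few diary days, whom step 1 assigns to MAR.
5. Correct the sentence in SAP 5.5.1, Step 1 that introduces the override as applying to subjects stopped by study termination. The flag definition below it says the opposite.

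The cost is a few sentences, one derived variable and a short code change. The reported mean reduction becomes slightly less favourable, and a conservative assumption is made for what may be only a few subjects.
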